1201 differences in adverse events when comparing women who participated with their partner compared to
1202 women who participated alone. A study in Zambia found that women participating in antenatal couple
1203 counseling did not experience more adverse social events associated with HIV disclosure
1204 (separation/divorce, forced to leave the home, violence) than women counseled alone.[180] In a
1205 randomized study in Tanzania, HIV-positive women in the couples voluntary testing and counseling arm
1206 had lower levels of marital dissolution and violence after testing than HIV-positive women in the
1207 individual counseling and testing arm.[84] Never-the-less, due to the potential risks of HIV status
1208 disclosure it is clear that home-based strategies need to be carefully designed.

1209
1210 Although we have not had problems in the past in our studies with couples in Nyanza, Kenya with
1211 participants reporting being there under coercion, staff members will be trained to be sensitive to the
1212 possibility that one member of the couple was pressured or coerced by the other partner to participate

1213 in the study. Questions may be posed such as "Did you come here freely?" or "Will something bad
1214 happen to you if you say no?" Should the staff member have this suspicion, s/he will be trained to
1215 immediately terminate the survey or session and provide the participant with appropriate referrals and
1216 the study incentive. Any data collected will be destroyed. The staff member will also be trained to offer
1217 the participant the opportunity to remain in the interview room for the appropriate amount of time that it
1218 would have taken to complete the survey or interview so that the study partner would not be alerted to
1219 the fact that the interview was terminated. If necessary, back-up staff members who are clinicians can
1220 be contacted to assess the appropriate immediate steps, should intervention be needed.
1221

1222 Should evidence of coercion arise in a couples' counseling session, the counselor will provide the
1223 appropriate clinical intervention regarding participation of the couple and provide community referrals.
1224 Should a participant specifically request an intimate partner violence referral, the staff member will
1225 immediately terminate the interview, provide the participant with the study incentive, offer to let the
1226 participant remain in the interview room for the approximate time of completion, and assist the
1227 participant in contacting an appropriate service agency. In addition, our resource list given to all
1228 participants will include intimate partner violence programs, clinicians, and support groups specializing
1229 in relationship abuse and violence.

1230 *Risks associated with HIVST kit distribution:* Our study will use procedures developed and utilized by
1231 co-investigators [name] and [name] to minimize probability of violence associated with participants'
1232 offering HIV testing to male partners and to minimize probability of adverse reactions to test results and
1233 ensuring receipt of appropriate services. To minimize the likelihood of violence against study
1234 participants, participants will be encouraged to distribute a test kit to their male partner or to use both
1235 test kits to undertake couples testing if they feel comfortable doing so; they will also be counseled
1236 on how to talk to their partners about HIV testing, the possibility of adverse reactions associated with
1237 suggesting HIV testing, learning their partner's HIV status, and disclosing their own HIV status.
1238 Study staff will be trained to talk to female participants at the time of enrollment about the importance of
1239 *using their discretion and assessing the risk of IPV* when deciding whether to introduce self-tests to
1240 their male partners. It will be emphasized to study participants that they are not obligated to distribute
1241 self-tests to their male partners. Participants will be counseled to never offer a self-test to someone who
1242 they will believe will become violent due to the introduction. Following Kenya's 2015 HIV testing
1243 services guidelines, participants will be informed about the need to seek clinic-based confirmatory
1244 testing if a reactive self-test result is obtained, and an invitation for confirmatory testing at a clinic
1245 will be included with each test. Information will also be provided on clinics in the area where free HIV
1246 care and treatment is available. Additionally, we will inform study participants on where they can seek
1247 help if experience mental distress, experience violence, or need other counseling or advice. The
1248 proposed study will utilize the training materials for study staff that were implemented during Drs.
1249 [name] and [name]'s studies on HIV self-testing with pregnant/postpartum women in this part of
1250 Kenya. Additionally, in our home-based couple visit pilot study, we set up intensive procedures and
1251 referral systems for participants experiencing IPV and mental distress.
1252

1253 *Risks related to couple home visits:* Home visits for those randomized to the home-based couples
1254 intervention arm of the study will be conducted in a manner such that we uphold the highest standards
1255 of confidentiality and prevent unwanted disclosure of HIV status in the community and the family. Prior
1256 to starting this phase of the study, community announcements will be made through the community
1257 partners, stating that the health facility will be starting home visits for pregnant women and male
1258 partners to support maternal and child health. Lay health workers conducting home visits will use
1259 unmarked vehicles and will not wear any garments that identify them as working on HIV/AIDS. When
1260 visiting the household, the lay health workers will request to speak to the couple alone in a private room
1261 in the household, or at a nearby location in the community, and will not begin the study explanations
1262 and informed consent process for the man until they have obtained this privacy. In each community, we
1263 will identify a location for couple sessions that participants may choose if privacy cannot be maintained
1264 in the home (such as the home of the local community health worker). The lay health worker will offer
1265 HIV counseling and testing to the couple together, as if the woman had not already tested for HIV at the
1266 ANC clinic. Our experiences with couple/family HIV counseling and testing in Uganda and South Africa

1267 reveal that most “index clients” (persons who initially tested HIV-positive in the clinic) prefer this
1268 approach.

1269
1270 *Risks associated with testing for HIV:* Engaging in voluntary counseling and testing for HIV, CHTC, will
1271 have a separate informed consent process, which will detail the potential risks, procedures involved,
1272 and any benefits. The risks associated with testing could include pain or complications from the finger
1273 prick in order to obtain serum for the rapid test. Testing will be conducted by trained HIV counselors,
1274 who are trained in phlebotomy and GCP in order to minimize the likelihood of any complications. There
1275 is a risk that participants could learn that they or their partner are HIV-positive. The testing counselors
1276 will be trained in all aspects of aiding participants through the testing process to alleviate as much
1277 distress as possible and to help them come to terms with this information. Additional referrals for
1278 couples’ counseling, services for HIV care and treatment, and other relevant services will also be
1279 provided as part of the intervention.

1280
1281 **Potential benefits of the proposed research to the subjects and others:**

1282 There are no direct benefits to the study participants. However, they may learn information regarding
1283 HIV treatment and prevention, pregnancy, and infant health, and may learn skills for communicating
1284 better with their partner, and potentially reduce their risk for HIV. The larger public health community
1285 could benefit if the intervention demonstrates efficacy, as improving rates of treatment and reducing
1286 levels of HIV viral load in individuals can potentially lower the burden of HIV in the community. There
1287 could be benefits to the mother and child with regard to increased likelihood of health care facility
1288 delivery, preventive healthcare utilization, and/or ART treatment for the pregnant women. While there
1289 are some risks to participating in the study, based on prior experience, we feel that the likelihood of
1290 participants experiencing negative events due to participation is low. It is our aim that participation in
1291 the intervention could serve to improve treatment and prevention for HIV, including the reduction of viral
1292 load levels, and possibly learn skills to improve relationships with one’s partner. The risk to individual
1293 participants is small, and the potential to provide information that could benefit the target population
1294 outweighs the risk.

1295 **Reimbursement of participants:** Each participant will be reimbursed for each assessment visit
1296 (questionnaires), but not for brief phone assessments and intervention activities. Each participant will
1297 receive approximately 500Kenyan Shillings (roughly 5 US dollars) per assessment. This reimbursement
1298 is in accordance with other studies being conducted through KEMRI, and will be approved by the local
1299 Kenyan IRB. Reimbursements will be paid in cash following the completion of each visit. Participants in
1300 the home visit study arm will also receive a small gift (such as a bar of soap or a bag of sugar) of
1301 approximately 200 KSh value (\$2.66 US) at each home visit, which is a cultural expectation for persons
1302 visiting the home of pregnant/postpartum couples.

1303
1304 Participants in the in-depth qualitative interviews will be reimbursed 500 Kenyan Shillings (KSh) for their
1305 transportation expenses related to participation in the interview, which is equivalent to around \$5 US
1306 dollars, which is approximately the cost of round-trip minibus fare from a long-range location.

1307
1308
1309 **EXPECTED APPLICATION OF RESULTS**

1310 This study could improve our ability to improve HIV prevention behaviors, identification of pregnant
1311 women and male partners infected with HIV, treatment engagement, and reduce viral load for pregnant
1312 women and their male partners, thereby reducing the likelihood of vertical and horizontal HIV
1313 transmission, among couples in western Kenya, a population at high risk for HIV. Most HIV infections in
1314 sub-Saharan Africa are occurring within primary partnerships.² Intervening with couples also increases
1315 the participation of men in HIV prevention activities, which have previously focused on women, and
1316 could contribute to a shift in community norms regarding gender and couple relations. The ability to
1317 reduce the likelihood of transmission with partnerships, as well as mother-to-child transmission of HIV,
1318 has the potential for high public health impact. Thus, through this study, we will gain evidence of the
1319 comparative effectiveness of these three different approaches to engaging couples on health
1320 behaviors and outcomes. Following completion of the study, we will be able to present to the

1321 Kenyan MOH and partners, for potential expansion of effective strategies to more sites across the
1322 country. If found to be effective, these strategies can also be adapted to other similar settings in
1323 sub-Saharan Africa, with important potential benefits for maternal, paternal, and infant health.
1324

1325 **LIMITATIONS**

1326 In the case that we are not able to recruit enough couples in a timely manner, due to decreasing HIV
1327 prevalence in the study counties or other factors, we have the ability to add additional study sites
1328 due to our strong relationships with Ministry of Health County teams (see Letters of Support).

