 528 information on topics covered, CHCT uptake and result, assessments of negative life events,
 529 including IPV (conducted with women and men individually),[142] other services provided, and
 530 process measures. This form, along with records of observations of visits by supervisors, will be used
 531 to assess intervention fidelity.
 532 ○ *Qualitative interviews*: Utilizing one-to-one interviews, we will qualitatively explore experiences and
 533 perceptions of the home-based couples intervention, as well as other influences on health behaviors
 534 and outcomes of younger women and of women experiencing IPV.
 535

TABLE 1. Factors to be Assessed in Data Collection

	Factors	Study measurements	Group and timing
PREDISPOSING FACTORS	Socio-demographics	Age, education, literacy, ethnicity, religion, occupation	All participants at baseline and follow-ups
	Relationship characteristics	Marital status, type of union (monogamous/polygamous), relationship duration	
	Household conditions	House type, ownership of household goods, persons living in household, food insecurity, alcohol use (ref AUDIT-C)	
	Pregnancy & fertility	Parity, gravidity, number of living children	
TRANS-FORMATION OF COUPLE	Couple relationship dynamics	Relationship Satisfaction[143], Dyadic Trust[144], Couple communication[145], Interpersonal closeness[146], Sexual Relationship Power Scale[147], Commitment[148]	All participants at baseline and follow-ups
MOTIVATION AND COUPLE COPING	Disclosure	Reports of disclosure to others from both partners[149]	
	HIV-related couple	Male partner support for MCH specific, social support[150], Couple communal coping[151], Network of Relationships Social Provision Scale (ref)	
OTHER POTENTIAL MODERATORS AND MEDIATORS	Pregnancy intendedness	One item measure of the intendedness of the current pregnancy[152]	All participants at baseline and follow-ups
	Perceptions of stigma	Anticipated stigma and perceived community HIV-related stigma scales[153, 154]	
	Stigma experience	Anticipated, enacted, and internalized HIV-related stigma[155]	
	IPV	Dyadic version of WHO intimate partner violence measure[156]	
	HIV treatment beliefs	Adaptation of the Beliefs about Medications Questionnaire[157]	
	Depression	PHQ-8[158]	
COUPLE HIV TESTING (PRIMARY OUTCOME)	Anxiety	GAD-7[159]	
	Couple HIV testing	Couples HIV testing uptake during observation period (Y/N)*	
	HIV re-testing	Re-testing for HIV during pregnancy and postpartum *	

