	New male HIV+ tests	Number of new HIV+ test results of male partners*	
HEALTH CARE UTILIZATION	Discordant couples	Number of new serodiscordant couples identified	
	PMTCT practices	Mother's use of ARVs for PMTCT *, Prophylactic ARVs for the infant *, infant feeding practices	
	Use of MCH services	Number of ANC visits*, Childbirth with a skilled attendant (Y/N), Postnatal check-ups*	
	PREP uptake	Initiation of PrEP	
	Woman's HIV care linkage and engagement	Time to linkage in HIV care, *Enrollment in HIV care (Y/N), *Self-reported ART adherence, [160] Number of HIV visits*	
	Man's HIV care linkage	Time to linkage in HIV care, * Enrollment in HIV care (Y/N), * Self-reported ART adherence, [160] Number of HIV visits*	
	Infant HIV testing	Date and result of infant HIV test *	
	Intervention content	Topics covered, services delivered, referrals made during couple visits	
PROCESS MEASURES			All intervention participants at follow-up

Participation	Number of couple home visits completed, number of HIV self-tests received/used		
Social consequences	Positive and Negative Life Events measures[142]		
Acceptability	Satisfaction with intervention components, intervention content, and mode of delivery, attitudes toward PrEP and HIV self-testing		
SECONDARY HEALTH OUTCOMES	Viral suppression	Viral Load < 200 copies (undetectable)*	All HIV-positive participants at baseline and follow-ups
	HIV-free child survival	Child alive and HIV-free at 18 months after the birth*	

* Measures to be confirmed through medical records

536

537

538 Inclusion/exclusion criteria

539 Our inclusion criteria are: (a) women at 36 weeks of pregnancy or less (b) 15 years of age or older (c)
 540 has been offered HIV testing at ANC, (d) is currently in a stable relationship with a male partner and
 541 living with that male partner, (e) has not yet participated in couple HIV testing during this pregnancy,
 542 and (f) not in an HIV-positive concordant relationship Male partners are the person identified by the
 543 pregnant woman as her primary male partner and should also be 15 years of age or older.

544

545 STATISTICAL/ANALYSIS PLAN

546 Sample size and power calculations

547 The couple testing uptake outcome (primary outcome) will be assessed including both HIV-positive and
 548 HIV-negative women/couples. All three arms will be compared with each other (3 comparisons), so our
 549 Type I error rate is $0.05/3 = 0.017$ (two-sided). With three repeated measurements (baseline, 3 months,

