 599 relationship dynamics and social consequences. We will refer to the parameter estimates for these
 600 three covariates as Estimates B. We will then determine the direct and indirect effects of the treatment
 601 on each of the outcomes in Aims 1 and 2, with
 602 corresponding standard error estimates
 603 determined using bootstrap methods as
 604 described by Whittle, et al.[165] These models
 605 can also be adjusted for any potential
 606 confounders that are discovered, although we
 607 expect the randomization to account for a
 608 majority of any potential confounding.

609 **Supplementary dyadic analyses for Aims 1**
 610 **and 2:** Analyses with intact dyads enable
 611 investigation of couple-based research
 612 questions of how relationship dynamics affect
 613 behavior change in partnerships. For example,
 614 we might investigate whether one's own
 615 relationship satisfaction or one's partner's
 616 relationship satisfaction is more associated
 617 with couple testing uptake. To that end, we will
 618 extend the analyses described above to
 619 include actor and partner effects for covariates
 620 and mediators. *Actor effects* describe the
 621 influence that one's standing on independent or mediating variables of interest (e.g., communication,
 622 intimacy) has on one's own dependent variables (e.g., virologic control) whereas *partner effects*
 623 describe the influence that one's standing on independent variables has on the dependent variables of
 624 one's partner (e.g., partner's virologic control). This technique illuminates the effects that partners in
 625 intimate relationships can have on both their and their partner's behavior. In order to fit an actor-
 626 partner interdependence model (APIM)[166] to our data, we will change our GEE model to a random-
 627 effects model so that we can include a random effect for each couple, that will allow us to divide the
 628 variation in outcomes into within- and between-couple effects. Auto-regressive errors will be assumed
 629 for the longitudinal measures.

630

631

TABLE 3. AIM 2 QUALITATIVE INTERVIEW TOPICS

Theme	Topics
Contraceptive Use	(1) Knowledge and use of contraceptives before current pregnancy and postpartum
Male partner support	(2) Support and dependability of male partner for maternal and child health
Health Care Utilization	(3) Barriers to utilization of health care services for pregnant women and partners

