Interventions	(4) perceptions of the home visits for couples and the HIVST kit interventions
IPV	(5) Perceptions of change in violence and the role of pregnancy and HIV in IPV
HIV Care and Treatment	(6) Perceptions of change in HIV care and treatment over pregnancy and postpartum

632 Qualitative data will be analyzed to elucidate themes and lessons to further inform our quantitative
633 analysis (Table 3). Interviews will be audio-recorded and transcribed, translated (if necessary), and
634 then coded and analyzed using a thematic analysis approach.
635

636 **Accounting for potential missing data.** We will also investigate and address incomplete data issues
637 in our sample. Missing data within and between each wave of measurement should be minimal due to
638 our careful interviewer training and cohort retention. However, intermittent missing responses are
639 inevitable and some participants will be lost to follow-up. Our GEE models for Aims 1 and 2 make the
640 assumption that missing data occur completely at random (MCAR). We will use univariate analyses
641 such as chi-square and t-tests to assess whether individuals with complete data for any given analysis
642 are different from those with incomplete data. These analyses will be extended to explore differential
643 attrition by intervention group membership using logistic regression or analysis of variance (ANOVA)
644 models. If our assumption of MCAR appears questionable, we will model the missingness pattern with
645 logistic regression to estimate the probability of each subject's data is missing, conditional on their
646 observed data. We can use these weights in an inverse-probability weighted GEE model and compare
647 the results to those produced from models using only the observed data.

648 **Sex as a biological variable.** This study includes both men and women all analyses described above
649 will be run separately by sex assigned at birth, with the exception of the dyadic analyses, which build in
650 participant sex intrinsically, since we will use APIMs for distinguishable dyads distinguished by gender.
651

652 **Cost-Effectiveness Analysis for Aim 3:** We will assess the cost-effectiveness of the home-based
653 couples intervention compared to two less resource-intensive strategies of HIVST kits and standard
654 care. We hypothesize that this community-based intervention will prove to be a cost-effective strategy

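### The dyadic plan fits an actor-partner model to couple testing, an outcome both partners share, so its four actor and partner coefficients are only two coefficients under different names

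*Combined protocol and SAP*

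**What the plan says.** The section on supplementary dyadic analyses for Aims 1 and 2 gives as its example whether a person's own or the partner's "relationship satisfaction is more associated" "with couple testing uptake. To that end, we will" add actor and partner effects to the Aim 1 and 2 models. For the actor-partner interdependence model (APIM), the GEE becomes a random "effects model so that we can include a random effect for each couple, that will allow us to divide the" "variation in outcomes into within- and between-couple effects. Auto-regressive errors will be assumed" for the repeated measures. The paragraph on sex as a biological variable adds that the dyadic analyses build in "participant sex intrinsically, since we will use APIMs for distinguishable dyads distinguished by gender".

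The table of factors to be assessed in data collection (the second of two tables numbered 1) defines the primary outcome as "Couples HIV testing uptake during observation period (Y/N", to be confirmed in medical records. The Aim 1 analysis uses all longitudinal measures of couple testing. Women and men are surveyed separately about testing. No section says whether the dyadic outcome is one value per couple or two partner reports.

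The section also mentions virologic control, one's own and the partner's, as an example of a dependent variable. Eligibility requires that the woman is "not in an HIV-positive concordant relationship".

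**The concern.** An APIM separates two effects of a predictor, one on a person's own outcome and one on the partner's outcome. This requires each partner to have an outcome of his or her own. A couple tests together or it does not, so both partners carry the same value. The path from her satisfaction to her testing and the path from her satisfaction to his testing then lead to the same event, and there is no variation between partners to divide.

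The stake is interpretation. The analysis could report an actor-versus-partner contrast that the row layout produces by itself, or describe as within-couple behaviour what is really change between waves or disagreement between two interviews. The section covers both aims, so it also takes in facility delivery and child survival, which exist once per couple, and maternal viral suppression, which exists only for the woman.

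**Working it through.** **The plan's own figure.** The documents give no figure for the dyadic model. The nearest is the Table 2 power for couple testing, which shows the unit the plan has in mind. Inputs are 300 couples per arm, 3 measurements, correlation 0.50 (also 0.10), alpha 0.017 two-sided, and 23% in Arm 3. With one record per couple per wave, effective n per arm = 300 x 3 / (1 + 2 x 0.50) = 450.

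For 31% versus 23%: SE = sqrt((0.31 x 0.69 + 0.23 x 0.77)/450) = 0.0295; z = 0.08/0.0295 - 2.387 = 0.33; power = 62.8%. For 33, 35 and 37% the same formula gives 83.5, 94.7 and 98.8%. Table 2 states 63, 84, 95 and 99%. At correlation 0.10 (effective n 750) it gives 86.8, 97.5, 99.7 and 100.0%, against 87, 97, 100 and 100% stated. The sizing therefore fits one value per couple per wave, not one per partner.

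**Step 1: the coefficients collapse.** Let y be the couple's outcome, x_w her score, x_m his, and u the couple effect.
- Her row: logit = a_w + A_w x_w + P_w x_m + u, outcome y.
- His row: logit = a_m + A_m x_m + P_m x_w + u, outcome y.

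Both rows share y and u, so the likelihood does not change if (a_w, A_w, P_w) is exchanged with (a_m, P_m, A_m). For any fixed couple SD the log-likelihood is concave in these coefficients, so its maximum has A_w = P_m and P_w = A_m. If the model is pooled over sex (one A, one P), the same argument forces A = P whatever the data show.

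**Step 2: numerical illustration.** Assumptions, not from the documents: 534 simulated couples (two arms of 267), scores correlated 0.4, intercept -0.9, generating slopes 0.5 (hers) and 0.2 (his). The logistic fits below have no couple effect; the two-row fit by sex uses couple-clustered standard errors.

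| Fit | Her score | His score |
|---|---|---|
| One row per couple | 0.739 (SE 0.119) | -0.009 (SE 0.109) |
| Two rows, by sex: woman's row | actor 0.739 | partner -0.009 |
| Two rows, by sex: man's row | partner 0.739 | actor -0.009 |

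Pooled over sex, actor = partner = 0.353. The contrasts A_w - P_m and P_w - A_m are zero, with zero variance, to rounding.

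**Step 3: the couple variance.** Profile log-likelihood of a random-intercept logistic model, 534 couples, assumed uptake about 30%, couple SD on the grid 0, 1, 2, 3, 5, 10, 20, 50, 100, 200.

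| Layout | Highest grid point for couple SD |
|---|---|
| One ever/never value, duplicated by partner | none: -364.1 at 10, -333.5 at 50, -327.9 at 200, still rising |
| Two reports, 5 couples disagree | 100 (-354.6; -354.8 at 50) |
| Two reports, 10 disagree | 50 (-375.2) |
| Two reports, 27 (5%) disagree | 10 (-432.4; -432.7 at 20) |
| Two reports, 53 (10%) disagree | 5 (-496.6; -497.6 at 10) |
| Two or three waves, correlation 0.50, one row per wave | 3 |
| The same waves, rows duplicated by partner | 5 |

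For the duplicated value, a couple contributes E(p^2) or E((1-p)^2). These are bounded by E(p) and E(1-p), and the bound is reached only as the SD grows without limit. With 160 of 534 couples positive, the bound is 160 ln(160/534) + 374 ln(374/534) = -326.0, which the likelihood approaches and never reaches.

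Two points follow. With partner reports, the estimate depends on how often the two interviews disagree. With repeated waves, copying each row for the second partner moves the SD from about 3 to about 5 although no information was added.

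**Step 4: virologic control.** Known concordant-positive couples are ineligible at enrolment. New male positive results are an Aim 1 outcome, and viral suppression is measured in all HIV-positive participants. Couples with two viral loads can therefore arise, but mainly through a male diagnosis made after randomisation, which the arms aim to change.

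**The case against.** The section is headed supplementary and introduces the couple-testing question only as something that might be investigated. The plan specifies dyads distinguished by gender, so her and his satisfaction stay separately estimable and the substantive question can be answered. The plan is also longitudinal and surveys the partners separately. All of this stands, and it limits the point to how the model is matched to the outcome.

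It also rules out stronger readings that a reader might infer:
- That the couple variance always diverges. It does so only for a single duplicated value; repeated waves or discordant reports give a finite estimate, though not one that measures partner behaviour.
- That the two rows would be counted as independent and standard errors would be too small. The plan includes a couple effect.
- That the virologic example is impossible. Concordance is barred at enrolment only, and an effect of his satisfaction on her virologic control needs only her to be HIV-positive.
- That auto-regressive structure cannot exist in a logistic mixed model. It can, as a latent process for example, but "Auto-regressive errors will be assumed" does not say which form is meant.

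The objection does not explain why an actor-partner split is applied to an outcome with no separate value for each partner.

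**Conclusion.** The concern holds as a mismatch between a stated method and its named outcome. For couple testing the four actor and partner coefficients reduce to two. A fit pooled over sex sets actor equal to partner, and the within-couple part cannot be read as a difference in the partners' behaviour. The same misfit affects facility delivery, child survival and maternal viral suppression.

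The collapse is algebraic and needs only that both partners' rows carry the same outcome. The coefficient values, the 30% uptake and the disagreement rates are illustrative assumptions. The documents do not show how many couples will have two viral loads, so no number is given here. No primary or secondary arm comparison, error rate or sample size depends on this analysis.

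**What to change.** Revise the dyadic section of the SAP as follows.
- For each dyadic model, state whether the outcome is a couple value or two partner reports, and its source.
- For outcomes that exist once per couple or for one partner only, use one row per couple (per post-baseline wave where repeated) in the marginal GEE logistic model already planned. Enter the woman's and the man's baseline scores as two predictors and test equality of their coefficients.
- Reserve the APIM for outcomes measured on each partner, such as HIV re-testing, care linkage and ART adherence, in couples where both partners have the outcome.
- Keep analyses of two-partner viral loads, but label them as a small subset formed after randomisation. Care linkage and ART adherence in both partners need the same label.
- For binary outcomes, replace the auto-regressive error statement with a named working correlation (exchangeable or unstructured) or a specified latent structure.

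The cost is SAP wording. The data are already to be collected, and the couple-level model is simpler than the one planned.
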